5.3.3. Sensitivity Analyses

Two sensitivity analyses of the primary effectiveness endpoint will also be performed based on the mITT population.

A summary of sensitivity analyses is presented in [Table 5-3](#).

Table 5-3 Missing Data Handling Rules for the Sensitivity Analyses of the Primary Endpoint

Endpoint	Sensitivity Analysis No.	Missing Data Handling Rule	Population	Methodology
ALJDS responder rate at Month 6	1	Use observed data only	Observed Primary Endpoint	Fisher's exact test
ALJDS responder rate at Month 6	2	Multiple Imputation	mITT excluding participants who were inadvertently unblinded to the EI or who did not have a baseline ALJDS score of 2 or 3	Multiple Imputation

5.3.4. Supplementary Analyses

Descriptive statistics for the primary endpoint will be summarized for the mITT population during the control period (ie, Month 1, 3, and 6 after study treatment for the treatment group and after randomization for the control group). Additionally, descriptive statistics for the primary endpoint will be summarized for the VT and VMT populations, which includes all visits after study treatment (ie, Month 1, 3, 6, 9 and 12 for the VT population and Month 1 and 3 after maintenance treatment for the VMT).

5.4. Secondary Effectiveness Endpoints Analysis

5.4.1. Secondary Effectiveness Endpoints

The secondary effectiveness endpoints are (1) GAIS responder at Month 6 as assessed by the EI, (2) GAIS responder at Month 6 as assessed by the participant, and (3) change from baseline in

Rasch transformed score of FACE-Q Satisfaction with Lower Face and Jawline at Month 6 during CP.

A GAIS responder is defined as a participant who shows improvement from baseline in the overall aesthetic assessment in jawline area, a rating of improved or much improved on the GAIS scale ([Table 5-4](#)).

The GAIS responder rates as assessed by the EI and by the participant at Month 6 will be analyzed using Fisher's exact test.

Table 5-4 **Global Aesthetic Improvement Scale**

Score	Grade	Description
2	Much Improved	Marked improvement in appearance
1	Improved	Improvement in appearance, but a touch-up or retreatment is indicated
0	No Change	The appearance is essentially the same as the original condition
-1	Worse	The appearance is worse than the original condition
-2	Much Worse	The appearance is much worse than the original condition

Each participant's responses to the 5 items on the FACE-Q Satisfaction with Lower Face and Jawline questionnaire will be summed and converted to a scale score that ranges from 0 to 100 (higher score indicates more satisfaction) using the algorithm developed by the FACE-Q scale developers (see [Section 6.5.1](#)). The analysis will be conducted using observed data (eg, no imputation for missing baseline or Month 6 FACE-Q scale scores).

5.4.2. Main Analytical Approach

For the secondary effectiveness endpoints of GAIS responder status at Month 6 as assessed by the EI and as assessed by the participant, the 95% CI will be provided for the proportion of responders within each treatment group, where applicable. These analyses will be performed on the mITT population.

No multiplicity adjustments will be made for the 2 GAIS responder rates since these endpoints are descriptive in nature.

For the secondary effectiveness endpoint of change from baseline in FACE-Q Satisfaction with Lower Face and Jawline overall score at Month 6 for the treatment group in the mITT population, a 2-sided paired t-test at the 5% level will be used to determine if the mean overall satisfaction score at Month 6 is statistically greater than that at baseline. This test will be

[figure not shown]
performed only if the co-primary endpoints are met. For items with missing data (which includes more than 1 response was selected, not applicable was selected, or a question was skipped), insert the mean of the completed items into the total sum score. If less than 50% of the questions have been answered (ie, number of missing items is 2 or more), then the overall score will be missing. The summary score including the imputation of missing items is rounded to the nearest integer and converted to the Rasch transformed score using the conversion table in Section 6.5.1.

Secondary effectiveness analyses are summarized in Table 5-5.

Table 5-5 Secondary Effectiveness Analyses

Endpoint	Description	Missing Data Handling Rule	Methodology
GAIS responder status as assessed by the EI at Month 6	Number (%) of responders by treatment group	Observed data is used; no imputation is needed	Categorical descriptive statistics
GAIS responder status as assessed by the participant at Month 6	Number (%) of responders by treatment group	Observed data is used; no imputation is needed	Categorical descriptive statistics
Mean change from baseline in Rasch transformed score of FACE-Q satisfaction with lower face and jawline at Month 6	Mean change from baseline within the treatment group	No imputation. Only observed data will be used in the analysis.	2-sided paired t-test

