# 8.3.2 Secondary Effectiveness Analyses

The following analyses will be performed for each of the secondary effectiveness endpoints:

- Responder rates with 95% CI for the treatment group based separately on the EI and subject assessments of GAIS, where a "responder" is a subject who shows improvement in the overall aesthetic assessment in jawline area (Improved or Much Improved on GAIS) at the Month 6 Visit.
- Descriptive summary of the change in overall score of subject's satisfaction with lower face and jawline since baseline at the Month 6 Visit based on the treatment group subjects' responses on the validated FACE-Q Satisfaction with Lower Face and Jawline questionnaire; a 2-sided paired t-test at the 5% level to demonstrate that the mean overall satisfaction score at Month 6 is statistically greater than that at baseline. This test is only performed if the primary endpoint is met.

No multiplicity adjustment will be made for the 2 GAIS responder rates since these endpoints are descriptive in nature.

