- ! For applicable effectiveness and safety endpoints, baseline is defined as the last non-missing value on or before the latter of randomization date or first treatment date in the control period, unless otherwise specified.
- ! Descriptive statistics for continuous variables include the sample size (N), number of non-missing observations (n), mean, standard deviation, median, 1st and 3rd quartiles, minimum, and maximum. For continuous data, a 2-sample t-test or Wilcoxon rank test will be used for between group comparisons as appropriate, unless stated otherwise. Specified that 95% CI for continuous variables will be based on the standard normal distribution in Section 5.1.
- ! Summary statistics for categorical variables include the sample size (N1), frequency count, and percentage. Ordinal categorical variables will be analyzed using the Cochran-Mantel-Haenszel test. Nominal variables will be analyzed using Pearson's chi-squared test or Fisher's exact test as appropriate. The 95% CI will be computed using the exact binomial method.
- ! The level of significance used for all statistical tests will be 0.05, 2-sided, unless stated otherwise.
- ! The change from baseline values will be computed as the value for the post baseline visit minus the baseline value, unless otherwise indicated.
- ! In the event if any data collected was after exit, it will not be included in tables but will only be presented in the listings.
- ! All statistical analysis will be performed using SAS version 9.3 or higher.
- ! MedDRA 22.1 or newer will be used to code AEs and medical history.
- ! WHO Drug Dictionary 201703 or newer will be used to code medications.

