6.5. Scales and Scoring Algorithms

6.5.1. FACE-Q™ – Satisfaction with Lower Face and Jawline Scale

For each question, circle only one answer. With your lower face in mind (lower cheeks and jawline), in the past week, how satisfied or dissatisfied have you been with:

	Very Dissatisfied	Somewhat Dissatisfied	Somewhat Satisfied	Very Satisfied
a. How prominent your jawline looks?	1	2	3	4
b. How sculpted (well-defined) your jawline looks?	1	2	3	4
c. How your jawline looks in profile (side view)?	1	2	3	4
d. How nice your lower face looks?	1	2	3	4
e. How smooth your lower face looks (i.e. no jowls or folds of fatty skin)?	1	2	3	4

Copyright©2013 Memorial Sloan-Kettering Cancer Center, New York, USA. All rights reserved.

The FACE-Q, authored by Drs. Andrea Pusic, Anne Klassen and Stefan Cano, is the copyright of Memorial Sloan Kettering Cancer Center (Copyright ©2013, Memorial Sloan-Kettering Cancer Center). The FACE-Q has been provided under license from Memorial Sloan Kettering Cancer Center and must not be copied, distributed or used in any way without the prior written consent of Memorial Sloan Kettering Cancer Center.

Note to Investigators: This scale can be used independently of the other scales. REDCap Data Dictionary files (<http://projectredcap.org/>) and SPSS syntax files are available.

Psychometric Paper: Klassen AF, Cano SJ, Scott AM, Pusic AL. Measuring outcomes that matter to facelift patients: development and validation of FACE-Q Appearance Appraisal Scales and Adverse Effects Checklist for the lower face and neck. Plast Reconstr Surg. 2014;133(1):21-30.

CONFIDENTIAL

JUVÉDERM VOLUX™ XC

Statistical Analysis Plan V25L-002

FACE-Q™ - SATISFACTION WITH LOWER FACE & JAWLINE CONVERSION TABLE

Instructions: Higher scores reflect a better outcome. If missing data is less than 50% of the scale's items, insert the mean of the completed items. Use the Conversion Table below to convert the raw scale summed score into a score from 0 (worst) to 100 (best).

SUM SCORE	EQUIVALENT RASCH TRANSFORMED SCORE (0-100)
5	0
6	9
7	16
8	22
9	28
10	34
11	40
12	46
13	52
14	59
15	66
16	72
17	78
18	84
19	92
20	100

**FACE-Q™ - SATISFACTION WITH LOWER FACE & JAWLINE INTERPRETATION
TABLE**

	Very Dissatisfied	Somewhat Dissatisfied	Somewhat Satisfied	Very Satisfied
a. How prominent your jawline looks?	0-14	14-39	39-81	81-100
b. How sculpted (well-defined) your jawline looks?	0-19	19-48	48-78	78-100

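### SAP 5.4.2 equates under 50% of the 5 FACE-Q items answered with 2 or more missing, but the correct count is 3 or more; SAP 5.4.1 also names a GAIS test that the rest of the plan does not support

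*SAP*

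**What the plan says.** **FACE-Q.** SAP 5.4.1 fixes the scale length ("Each participant's responses to the 5 items on the FACE-Q Satisfaction with Lower Face and Jawline questionnaire") and says the sum is converted to a 0–100 score "using the algorithm developed by the FACE-Q scale developers", pointing to SAP 6.5.1. The instruction there is: "If missing data is less than 50% of the scale's items, insert the mean of the completed items". SAP 5.4.2 also fills missing items with the mean of the completed ones, then sets a limit beyond which the overall score is missing: "If less than 50% of the questions have been answered (ie, number of missing items is 2 or more". The resulting change from baseline at Month 6 goes into a two-sided paired t-test in the treatment group, run only if the primary is met (SAP 5.4.2, Table 5-5; Protocol 8.3.2).

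**GAIS.** SAP 5.4.1 states: "The GAIS responder rates as assessed by the EI and by the participant at Month 6 will be analyzed using Fisher's exact test". SAP 5.4.2 gives only within-group confidence intervals, where applicable, and adds: "No multiplicity adjustments will be made for the 2 GAIS responder rates since these endpoints are descriptive in nature". Table 5-5 lists descriptive statistics and no test. Protocol 8.3.2 plans "Responder rates with 95% CI for the treatment group based separately on the EI and subject assessments of GAIS". The list of departures from the protocol in SAP 6.2.1 does not mention a GAIS test.

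**The concern.** The percentage in SAP 5.4.2 and the count offered as its equivalent cannot both hold on a 5-item scale, and the count also disagrees with the scoring algorithm the SAP adopts. A programmer who codes the count discards a baseline or Month 6 form with exactly 2 missing items and so loses that participant from the paired t-test. A programmer who codes the percentage, or SAP 6.5.1, fills the two items and keeps the participant. The SAP counts skipped items, multiple responses and not-applicable answers all as missing, so the rule can come into play in several ways. FACE-Q change is the only secondary endpoint with a hypothesis test gated on the primary, so its analysis set should not depend on which half of a sentence is followed.

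The GAIS sentence is a separate matter of consistency. It promises a test for two endpoints that the rest of the plan describes without one, and for the participant rating there is no control group to compare with.

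**Working it through.** **Inputs.** 5 items (SAP 5.4.1, 6.5.1); the limit in SAP 5.4.2; the fill-in rule in SAP 6.5.1; 144 to 162 randomized to treatment and 15% drop-out by Month 6 (Protocol 8.5, SAP 3). Item-missingness rates are assumed.

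**Step 1: can the plan's count be reproduced?** Share answered = (5 − m)/5 for m missing items.

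| Missing m | Answered | Percentage in 5.4.2 | Count in 5.4.2 | 6.5.1 |
|---|---|---|---|---|
| 0 | 100% | score | score | score |
| 1 | 80% | score | score | score |
| 2 | 60% | score | **missing** | score (40% missing) |
| 3 | 40% | missing | missing | not scored (60% missing) |
| 4 | 20% | missing | missing | not scored |
| 5 | 0% | missing | missing | not scored |

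The count is not reproduced. Reading the limit as 50% or less, instead of less than 50%, also gives 3. Among scales of 3 to 8 items, 2 or more missing matches less than 50% answered only for 3 items.

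**Step 2: how often would it matter?** Assume each item is missing independently with probability p, on both the baseline and the Month 6 form.

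- Exactly 2 missing on one form: 10 × p² × (1 − p)³.
- Pairs lost only through the count: P(≤2 missing)² − P(≤1 missing)².
- Treatment-group participants at Month 6: 144 × 0.85 ≈ 122 to 162 × 0.85 ≈ 138.

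| p | Exactly 2 missing, per form | P(≤2)² − P(≤1)² | Pairs lost | Of 122–138 |
|---|---|---|---|---|
| 1% | 0.10% | 0.99999² − 0.99902² | 0.19% | 0.24–0.27 |
| 2% | 0.38% | 0.99992² − 0.99616² | 0.75% | 0.92–1.04 |
| 5% | 2.1% | 0.99884² − 0.97741² | 4.2% | 5.17–5.85 |

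The 5% row is a high assumption: it implies that 1 − 0.95⁵ = 23% of forms have at least one missing item.

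**Step 3: GAIS data against the GAIS test.**

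- *Control period.* Protocol Table 4 and the synopsis description of the control group schedule GAIS by the EI at Months 1, 3 and 6, with no participant GAIS.
- *Delayed treatment.* Control participants first rate GAIS in Protocol Table 5, after they have been treated. SAP 5.4.2 places the GAIS analysis on the mITT population, which SAP 5.1 uses for the control period as randomized, so these later ratings cannot serve as control data.
- *Result.* For participant GAIS at control-period Month 6 the control n is 0, so a between-group Fisher's test cannot be run. For EI GAIS it can be run, but SAP 5.4.2, Table 5-5 and Protocol 8.3.2 do not plan it.

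**The case against.** The strongest reply is that this is a slip with a recoverable intent. SAP 5.4.1 names the developers' algorithm, SAP 6.5.1 states it, and the percentage in SAP 5.4.2 agrees with both, so only the parenthesis is out of line. The consequence is also small: even losing 6 of 138 pairs would widen the standard error by only about 2% (√(138/132) = 1.02), and the 5% scenario needs the 23% of incomplete forms shown above. All of this stands as a comment on size. It does not remove the error, because the parenthesis gives an explicit count that a programmer can code directly, and no text says which wording prevails. A stricter rule of at most one missing item may have been intended. In that case the percentage is wrong, and the departure from SAP 6.5.1 is undeclared.

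On GAIS, an unadjusted Fisher p-value can sit beside a descriptive rate, and SAP 5.1 lists Fisher's test among the defaults for nominal variables. For EI GAIS the problem is therefore one of alignment, not of validity. For participant GAIS, the qualifier in SAP 5.4.2 (where applicable) covers the confidence intervals only; the Fisher sentence in SAP 5.4.1 has no such limit.

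**Conclusion.** Both points hold. On 5 items, the count in SAP 5.4.2 contradicts its own percentage and SAP 6.5.1; the count consistent with both is 3 or more missing. The effect is confined to forms with exactly 2 missing items. At assumed item missingness of 1–2% it amounts to about one participant or fewer; at 5% it is between five and six. These figures rest on independent missingness at rates the documents do not give. Nothing shows that the FACE-Q conclusion would change.

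The Fisher's test cannot be carried out for participant GAIS, and its status for EI GAIS is unclear. Neither point touches the primary endpoint or the sample size. Correction before analysis is still warranted, because the first point is an explicit rule for a gated test that is wrong as written.

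**What to change.** **FACE-Q.** In SAP 5.4.2, replace 2 or more with 3 or more. If a stricter limit is intended, restate the percentage to match it and declare the departure from SAP 6.5.1.

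**GAIS.** Delete the Fisher sentence in SAP 5.4.1 and report Month 6 responder rates with the intervals already specified in SAP 5.1 ("The 95% CI will be computed using the exact binomial method"): both groups for the EI rating, treatment group only for the participant rating. Alternatively, keep Fisher's test for EI GAIS only, label it descriptive and without multiplicity control, add it to Table 5-5, and list it in SAP 6.2.1 as a change from Protocol 8.3.2.

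**Cost.** Two wording edits for the main option, and a few more cross-reference edits for either alternative. No participants, visits or data are needed.

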5.5. Other Effectiveness Endpoints Analysis

CONFIDENTIAL
JUVÉDERM VOLUX™ XC

[figure not shown]
Statistical Analysis Plan V25L-002

CONFIDENTIAL
JUVÉDERM VOLUX™ XC

Statistical Analysis Plan V25L-002

Table 5-6 Other Effectiveness Analyses

5.6. Safety Analyses

5.6.1. Extent of Exposure

Treatment exposure-related variables will be summarized for the VT and VMT populations.

Study treatment exposure will be measured by volume injected at each treatment (Table 5-7).

Table 5-7 **Exposure to Study Treatment**

Endpoint	Description	Timing	Methodology
Volume injected ! Chin ! Right and left pre-jowl area ! Right and left post-jowl area ! Right and left marionette lines ! Right and left angle of the mandible ! Right pre-jowl + post-jowl + marionette + angle of mandible ! Left pre-jowl + post-jowl + marionette + angle of mandible ! Total	Summary by treatment group, treatment (initial, touch-up, maintenance, initial and touch-up combined), and side of jawline	Initial, Touch-up, Maintenance, Initial and Touch-up combined	Continuous descriptive statistics

5.6.2. Administration of Study Treatment

The number of participants who received treatment anesthesia will be summarized for the VT and VMT populations by treatment group. Variables related to administration of treatment listed in Table 5-8 will be summarized for the VT population by treatment group for both sides of the jaw combined at the initial and the touch-up treatments, and for the VMT population for both sides of the jaw combined at the maintenance treatment.

Table 5-8 Administration of Study Treatment

Endpoint	Description	Timing	Methodology
Pre-treatment Anesthesia type ! Ice ! Topical ! Local anesthesia	Summary by treatment group and treatment (initial, touch-up or maintenance)	Initial, Touch-up, Maintenance	Categorical descriptive statistics
Pre-treatment anesthesia duration (minutes) ! Anesthesia duration is computed as injection time minus start of anesthesia administration time. Summarize by treatment group, treatment, and anesthesia type.	Summary by treatment group and treatment (initial, touch-up or maintenance)	Initial, Touch-up, Maintenance	Continuous descriptive statistics
Treatment administration ! Planes of injection (chin, right and left pre-jowl area, right and left post-jowl area, right and left marionette lines, right and left angle of the mandible) ! Injection technique (chin, right and left pre-jowl area, right and left post-jowl area, right and left marionette lines, right and left angle of the mandible) ! Route of administration: needle only or cannula (chin, right and left pre-jowl area, right and left post-jowl area, right and left marionette lines, right and left angle of the mandible) ! Number of needles used ! Device/Needle problem or malfunction	Summary by treatment group and treatment (initial, touch-up or maintenance)	Initial, Touch-up, Maintenance	Categorical descriptive statistics and Continuous descriptive statistics
Treatment Characteristics ! Injection ease ! Product Moldability	Summary by treatment group and treatment (initial or touch-up)	Initial and Touch-up	Categorical descriptive statistics and Continuous descriptive statistics

5.6.3. Adverse Events

An AE will be considered a TEAE if the AE began or worsened (increased in severity or became serious) on or after the date (and time, if known) of the initial treatment for the treatment group and on or after the date of randomization for the control group. An AE will be considered a TESAE if it is a TEAE that additionally meets any SAE criterion.

A TEAE will be considered a treatment-related AE if the TEAE is deemed related to the procedure or the study device by the TI.

CONFIDENTIAL

JUVÉDERM VOLUX™ XC

Statistical Analysis Plan V25L-002

An AESI is defined as any vision-related TEAE. The incidence of AESI will be summarized separately for CP, TP, and RP in descending order of PT, if the total number of participants with AESI is at least 5.

Overall summary will be provided on a per-participant level for TEAEs, treatment-related TEAEs, TESAEs, deaths, and TEAEs leading to study intervention discontinuation. If more than one event is coded to the same PT for the same participant, the participant will be counted only once for that PT using the greatest severity for the summarizations by severity and most related occurrence for the summarizations by relationship to study intervention. If the severity of a TEAE is missing, the maximum severity will be assigned to the event for the summarization by severity. The value will be displayed as missing in the data listing. If the relationship to the study intervention is missing for a TEAE, the event will be considered related to the study intervention for the summarization. The value will be displayed as missing in the data listing.

TEAEs will be summarized by treatment group for CP using the Safety population. TEAEs will also be summarized for TP and RP using the VT and VRT populations, respectively.

The number and percentage of participants with TEAEs and the events in the following AE categories will be summarized for the above populations as described in [Table 5-10](#). For participants who received maintenance treatment, their AEs reported during the three months in the initial treatment period will be summarized and presented in parallel with AEs reported during the maintenance treatment period.

Summary tables will be provided for participants with TESAEs and participants with TEAEs leading to discontinuation if these occurred in 5 or more participants. Listings of all TEAEs, AESIs, TESAEs, TEAEs leading to discontinuation, and death will be presented.

AEs that occur after obtaining written informed consent but before treatment will be listed, but not summarized.

The duration of an AE is defined as the end date of AE minus the start date of AE, plus 1.

Table 5-9 TEAE Summaries

Endpoint	Description	Timing	Methodology
Overall summary	Overall summary only for the following categories: ! TEAEs ! Treatment-related TEAEs ! Treatment-related TEAEs at injection site ! Treatment-related TEAEs not at injection site ! TESAEs ! Treatment-related TESAEs ! Treatment-related TESAEs at injection site ! Treatment-related TESAEs not at injection site ! Discontinued due to TEAE ! Deaths	CP, TP, MP	Categorical descriptive statistics, event descriptive statistics
TEAEs	! Overall summary and by SOC and PT ! Overall summary and by SOC, PT, and maximum severity	CP, TP, MP	Categorical descriptive statistics, event descriptive statistics
Treatment-related TEAEs	! Overall summary and by SOC and PT ! Overall summary and by SOC, PT, and maximum severity ! Overall summary by maximum severity, time to onset, duration, action taken, and outcome	CP, TP, MP	Categorical descriptive statistics, event descriptive statistics
TESAEs	Overall summary and by SOC and PT	CP, TP, MP	Categorical descriptive statistics, event descriptive statistics
AEs leading to discontinuation	Overall summary and by SOC and PT	CP, TP, MP	Categorical descriptive statistics, event descriptive statistics

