### 8.3.3 Other Effectiveness Analyses

# 8.3.4 Safety Analyses

Subject assessment of procedural pain score and of jaw function using the 20-item Jaw Functional Limitation Scale questionnaire will be summarized descriptively. Assessments from the pronunciation recordings and facial sensation assessment will be summarized descriptively.

Snellen visual acuity, confrontational visual fields, and ocular motility assessments will be summarized descriptively.

ISRs will be summarized by maximum severity and ISR days for initial, touch-up, and maintenance treatments, separately. Summaries will include the incidence rate for each ISR.

Treatment-emergent AEs and treatment-related AEs (ie, device- or procedure-related) will be summarized by System Organ Class and Preferred Term, and severity. In addition, treatment-related AEs will also be tabulated by duration, severity, causality, action taken, and outcome. The summary will include incidence rate as well as total number of events.

AEs that occur after obtaining written IC but before treatment will be listed, but not summarized.

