3. Sample Size Determination

Sample size is determined to provide adequate power to demonstrate that the product is effective as well as safe. A sample size of 120 participants in the treatment group and 40 participants in the control group will provide > 99% power to detect a difference of at least 40% in the responder rates between the 2 groups. This calculation is based on a 1-sided Fisher's exact test at the 2.5% level. The treatment group is assumed to have at least an 80% responder rate and the control group is assumed to have at most a 40% responder rate. Assuming a screen fail rate of 25% and a drop-out rate of 15% between randomization and the Month 6 visit, up to 280 participants will be enrolled, with at least 144 participants and at most 162 participants randomized to the treatment group and at least 48 participants and at most 54 participants randomized to the control group (3:1 ratio).

This sample size is considered adequate to determine the safety profile of the product in the jawline area. Assuming a screen fail rate of 25%, a 5% drop-out rate between randomization and initial treatment for the treatment group, and a 15% drop-out rate between randomization and optional treatment for the control group, it is estimated that at least 176 subjects will be treated in the study. With 176 treated subjects, there is at least 92% power to detect an AE related to treatment with an incidence rate of 1.5% in the population using a 1-sided exact binomial test at the 2.5% level.

The commercial software, PASS (2008, Version 8.0.13), was used for the power calculation. The sample size calculation used an inequality test for 2 proportions to demonstrate that the treatment group is superior to the control group. The safety calculation used an inequality test for 1 proportion.

4. Populations for Analysis

The 5 analysis populations will consist of participants as defined in [Table 4-1](#).

Table 4-1 Analysis Populations

Population	Definition	Study Treatment Assignment
mITT	All randomized participants with non-missing baseline on the ALJDS scale on both sides of the jaw	As randomized
Observed Primary Endpoint	All mITT participants who have Month 6 assessment on the ALJDS scale on both sides of the jaw	As randomized
Safety	All randomized participants who receive study treatment (VOLUX or control)	As treated ^a

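### SAP 5.6.3 counts a blank causality field as treatment-related even in controls not yet injected, and its rule on events before treatment does not match its control-group TEAE definition

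*SAP*

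**What the plan says.** SAP 5.6.3 starts treatment-emergent events at the initial treatment for the treatment group and "on or after the date of randomization for the control group". It then orders the comparison: "TEAEs will be summarized by treatment group for CP using the Safety population". Table 5-9 gives CP as a timing for the treatment-related rows, among them "Treatment-related TEAEs at injection site".

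An event is treatment-related "if the TEAE is deemed related to the procedure or the study device by the TI". For blanks the rule is: "If the relationship to the study intervention is missing for a TEAE, the event will be considered related to the study intervention". The listing still shows the value as missing. Within a preferred term, a participant is counted once, at the most related occurrence.

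Later in the same section: "AEs that occur after obtaining written informed consent but before treatment will be listed, but not summarized". Protocol 8.3.4 has the same rule: "AEs that occur after obtaining written IC but before treatment will be listed, but not summarized". Neither sentence says what it means for a control.

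**The concern.** Protocol 4.3.2 gives the control as no treatment. Until the optional treatment, a control has had no device and no treatment procedure, so under the SAP's own definition no control-period event can be related to either. A blank that becomes related is therefore a false count in that column. Treating missing as related is a cautious convention for people who were injected. For people who were not, it has no such justification.

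The CP table is the only concurrent randomized safety comparison in the trial, and its control arm is small, so single participants show.

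The listing-only sentence raises a second question. If treatment means injection, everything that happens to a control during CP comes before treatment, yet the same section says to tabulate it.

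Elsewhere the SAP adds control wording: in the TEAE definition, in prior and concomitant medication (5.6.6), and in AE start-date imputation (6.4.2.1). These two rules lack it.

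**Working it through.** **Inputs**
- Arm sizes: 48 to 54 controls and 144 to 162 in the treatment group (Protocol 5.1 and 8.5, SAP 3).
- Correct number of treatment-related events in uninjected controls: 0 (Protocol 4.3.2 with the definition in SAP 5.6.3).
- Share *a* of controls with at least one TEAE in CP: not given; assumed 10% to 40%.
- Share *b* of those with a blank relationship: not given; assumed 1% to 10%.
- All randomized controls are taken as the denominator of the CP control column, as in Protocol 8.1.

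**1. The plan's own safety figures.** Treated: 144 × 0.95 = 136.8 and 48 × 0.85 = 40.8; rounding each down gives 136 + 40 = 176, as stated. Chance of at least one event at 1.5% incidence: 1 − 0.985^176 = 0.930, against the stated 92% or more. Neither figure uses causality coding or control-period events, so neither moves.

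**2. Weight of one blank.** Control: 1/54 = 1.9% to 1/48 = 2.1%. Treatment group: 1/162 = 0.6% to 1/144 = 0.7%. With 3:1 allocation, one control weighs three times as much.

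**3. Expected false count in controls.** With *n* controls, the expected count is *n* × *a* × *b*, the expected rate is *a* × *b*, and the chance of at least one is 1 − (1 − *ab*)^*n*.

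| n | a | b | expected count | rate | chance of at least one |
|---|---|---|---|---|---|
| 48 | 10% | 1% | 0.05 | 0.1% | 5% |
| 48 | 20% | 5% | 0.48 | 1.0% | 38% |
| 54 | 40% | 10% | 2.16 | 4.0% | 89% |

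**4. Net effect on the group difference.** Let *u* be the share of VOLUX participants, and *v* the share of controls, counted as related only because of a blank. The displayed difference changes by *u* − *v*. The documents give neither share, so the sign is not determined.

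**5. The listing-only sentence against the other rules.**
- Literal reading: for controls who take optional treatment, CP ends on that treatment date (SAP Table 5-1); the others are never injected. All CP events of 48 to 54 controls (up to 48 × 0.5 = 24 to 54 × 0.5 = 27 person-years) would be listed only, leaving the control column empty.
- Reading with the TEAE definition: events from randomization are tabulated and none are removed.
- Under both readings, control events between consent and randomization are listed only, which is ordinary practice.
- For the second reading: the TEAE definition names the control group; the CP summary is by group; Table 5-9 includes CP; SAP 6.2.1 item 4 puts CP safety summaries on the mITT and Safety populations; SAP 6.4.2.1 imputes missing control onset dates to randomization; and SAP Table 4-1 counts control as a study treatment received.
- For the first: the TEAE definition itself sets initial treatment in one group against randomization in the other, so there the word means injection. Protocol 8.3.4 has the sentence without any control-specific TEAE definition beside it.

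**The case against.** The strongest reply on the blanks is that there should be hardly any. Protocol 11.1.9 requires the investigator to determine relationship and forbids delegation. Protocol 11 puts relationship on the AE form, 12.4.2 makes the principal investigator responsible for proper recording, and 12.6 has the sponsor review forms for completeness. This stands and keeps the effect small. It does not rescue the rule, which exists for the blanks that remain and gives a wrong answer for every one in an uninjected control.

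A reader might infer that blanks are the norm for controls and that the false rate could approach the 38.7% treatment-related rate reported for V25L-001. The documents do not support that. The AE form is not among them, mandatory causality points the other way, and 38.7% comes from another study over a different period.

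A reader might also infer that the rule shrinks the VOLUX excess. It does push the control rate up, but blanks in the VOLUX column become related too, so the net direction is not shown.

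Finally, a reader might infer that the listing-only sentence removes control events from the tables. The specific rules outweigh one general sentence carried over from the protocol. What stands is a wording conflict inside one section.

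**Conclusion.** The missing-means-related rule is wrong for controls before any injection. Each affected control adds a false 1.9 to 2.1 percentage points to a rate whose correct value is 0. On the assumed ranges (10% to 40% of controls with a TEAE, 1% to 10% of those with a blank), 0.05 to 2.2 participants are expected, or 0.1% to 4.0% of the control column. These ranges are illustrative; only the weight per participant follows from the documents.

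The listing-only sentence is an unreconciled conflict. Inclusion of control events is the likelier reading, and under it nothing is lost.

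The consequence is limited: the AE tables are descriptive, the blanks and the events remain in listings, and no primary result, test or power figure depends on either rule. The correction is still worthwhile because it removes a known false count at almost no cost.

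**What to change.** 1. SAP 5.6.3: apply missing relationship = related only to TEAEs with onset on or after a VOLUX injection. For events in participants not yet injected, leave a blank out of the treatment-related count, show it as missing in the listing, and keep any causality the TI actually recorded. Setting every control to not applicable would overwrite recorded judgements and goes beyond the defect. Tying the rule to injection also covers controls treated by mistake, a case foreseen in Protocol 8.1 and SAP 6.2.2 item 5.
2. SAP 5.6.3 and Protocol 8.3.4: align the listing-only sentence with the TEAE definition, so that it covers events before the initial treatment in the treatment group and before randomization in the control group.

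Cost: one programming condition, two SAP sentences and one protocol clarification. VOLUX blanks still count as related, so the convention stays cautious where it has a purpose.
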